### 8.3.6 Pregnancy

**A participant's participation is to be terminated immediately if a pregnancy is supposed (i.e. in case her pregnancy test becomes positive).**

The investigator must report to the sponsor any pregnancy occurring in a female study participant during her participation in this study. The outcome of the pregnancy should be followed up carefully, and any outcome of the mother and the child at delivery should be

reported. Abnormal pregnancy outcomes (e.g., spontaneous abortion, fetal death, stillbirth, congenital anomalies, ectopic pregnancy) are considered SAEs.

For a pregnancy in the partner of a male study participant, all efforts will be made to obtain similar information on course and outcome, participant to the partner's consent.

For all reports, the forms provided are to be used. The investigator should submit them within the same timelines as a SAE (see Section 8.3.5). Send the completed pregnancy forms to:

PPD [redacted] or Fax: PPD [redacted] (in the USA)

#### **8.4 Treatment of Overdose**

For this study, any dose of study intervention greater than single dose study intervention within a 12-hour time period will be considered an overdose.

The sponsor does not recommend specific treatment for an overdose.

In the event of an overdose, the investigator/treating physician should:

- Contact the Medical Monitor immediately;
- Closely monitor the participant for any AE/SAE;
- Document the quantity of the excess dose as well as the duration of the overdose in the CRF.

#### **8.5 Pharmacokinetics**

Pharmacokinetic parameters are not evaluated in this study.

#### **8.6 Pharmacodynamics**

Pharmacodynamic biomarker parameters are not evaluated in this study.

#### **8.7 Genetics**

Genetic testing is not performed in this study.

#### **8.8 Biomarkers**

Biomarkers are not evaluated in this study.

#### **8.9 Health Economics**

Health Economics/Medical Resource Utilization and Health Economics parameters are not evaluated in this study.

### **9. Statistical Considerations**

Statistical analysis will be performed using statistical analysis software (SAS) and the version used will be specified in the Statistical Analysis Plan (SAP) and placed on file. The SAP will

contain a more comprehensive explanation than described below of the methodology used in the statistical analyses. The SAP will also contain the rules and data handling conventions used to perform the analyses, and the procedure used for accounting for missing data.

### **9.1 Statistical Hypotheses**

The primary efficacy endpoint is the sum of change in pain intensity from 0 to 8 hours (SPID0-8). No multiplicity adjustment will be made. All statistical comparisons will be made at significance level of 0.05.

### **9.2 Sample Size Determination**

The study is not statistically powered. From operational feasibility point of view, a total of approximately 180 participants (30 participants per active treatment arm and 15 in the caffeine and placebo arms using a 2:2:2:2:1:1 ratio) are chosen, a total of approximately 190 participants will be randomized into the study if a drop-out rate of 5% is assumed.

### 9.3 Populations for Analyses

For purposes of analysis, the following populations are defined:

Population	Description
Safety	All participants who are randomized and take at least one dose of investigational product. Safety measures will be analyzed for all participants in the safety population.
Intent-To-Treat (ITT)	All participants in the Safety Population who provide at least one pain assessment after the first dose of the investigational product. ITT population will be used as secondary to conduct the sensitivity analysis for the selected parameters.
Per Protocol (PP) Population	
PP population will include all participants in ITT who do not have any major protocol violations and complete the 12 hour assessments. PP population will be used as the primary analysis for the efficacy parameters.
 
Major protocol deviations will be identified prior to database lock and may include but are not limited to significant violations of inclusion/exclusion criteria, noncompliance of the trial treatment taken, conditions such as vomiting and diarrhea or use of prohibited medications, and not following clinical trial protocol procedures. Any participant who rescues or vomits at or prior to 60 minutes after ingesting study medication will be excluded from the PP population.

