**1.3 Schedule of Activities (SoA)**

Protocol Activities	Screening Visit (within 28 days prior to oral surgery)	Dosing Period Inpatient	End of Trial Call or Visit (2-5 days after discharge)
		Day 1	
Written Informed Consent	X		
Inclusion/Exclusion Reviewed	X	X	
Medical/Medication History (incl. caffeine consumption)	X	X	
Physical and Oral Examination	X		
Vital Signs a	X	X	
Urine for Drug Screen	X	X	
Breath or saliva alcohol test	X	X	
Dental x-ray examination	X		
Urine Pregnancy Test (if applicable)	X	X	
Admission to Unit		X	
Oral surgery (between 0530 h and 1030 h)		X	
Randomization Number Assigned		X	
Investigational Product Administration		X	
Surgical Trauma Rating		X	
Stop watch method (perceptible and meaningful relief)		X	
Categorical Pain Rating Scale b		X	
Pain Intensity Numerical Rating Scale (NRS) c		X	
Categorical Pain Relief Rating Scale c		X	
Global Assessment of Pain Relief d		X	
Concomitant Medications		X	X
Adverse Events Assessed	X	X	X
Discharge from Unit the evening of Day 1		X	

a vital signs ( blood pressure, pulse rate, and respiration after sitting for at least 5 minutes). On Day 1, vital signs are due pre-operatively, post-surgery at 1 hour, and 12 hours after study medication dosing.

b to be completed prior to dosing

c Pain Intensity NRS to be completed at baseline (predose), and Pain Intensity NRS and Categorical Pain Relief will be assessed 0.5, 1, 1.5, 2, 3, 4, 5, 6, 7, 8, 9, 10, 11 and 12 hours postdose. If rescue occurs, scales/questions will be completed immediately each time rescue medication is taken

d assessment will be completed immediately before first rescue medication is taken or at 12 hours post-dose

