#### 8.1.6 Postsurgery

During the post-surgery recovery period, participants will rest quietly, but will be encouraged not to fall asleep. Participants will be permitted to drink clear liquids following surgery. Participant may incorporate foods according to a soft diet following dosing beginning 60 minutes after dosing. Participants will not be allowed to eat 30 minutes prior to any planned assessments.

In order to qualify for randomization and continue in the trial, participants must have 'moderate' or 'severe' postoperative pain intensity on the Categorical Pain Rating Scale **and** a score of  $\geq 5$  on the NRS within 4.5 hours of the last suture.

Eligible participants will be assigned a participant randomization number and investigational products will be administered according to a generated randomization schedule (see Section 6.1.1).

Participants who have not met the randomization criteria within 4.5 hours from last suture or 14:30 h will not be randomized and may be discharged from the clinic, once deemed eligible by an Investigator. Prior to being released from the clinic, discharge procedures will be reviewed with the participant. When discharged, all participants will need to make prior arrangements for travel and should not drive themselves home.

After the baseline (pre-dose) pain intensity is determined, pain intensity and pain relief will be rated by participants at 0.5, 1, 1.5, 2, 3, 4, 5, 6, 7, 8, 9, 10, 11, and 12 hours (+/-5 minutes over the first 6 hours; +/-5 minutes from hours 7 through 12) post-dose, and immediately prior to the use of the first dose rescue medication.

CCI

CCI [REDACTED]

CCI [REDACTED]

CCI [REDACTED]

This answer will be recorded by the study coordinator in the case report form. CCI [REDACTED]

CCI [REDACTED]

CCI [REDACTED]

CCI [REDACTED]

Participants will stay awake during the entire 12 hour assessment. The order of the pain assessments is Pain Intensity, then Pain Relief, then query about any AEs. At hour 12 or immediately prior to the first dose of rescue medication (if prior to hour 12), study participants will be asked to provide a Global Assessment of investigational product after completion of the other assessments. Additionally, participants will have vital signs taken after surgery then at 1 and 12 hours post-dose.

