#### 9.4.1 Efficacy Analyses

For each post-dose time point, Pain Intensity Differences (PID) will be derived by subtracting the pain intensity at the post-dose time point from the baseline intensity score (baseline score – post-baseline score). A positive difference is indicative of improvement. Time-weighted Sum of Pain Intensity Differences (SPIDs) will be calculated for 2, 4, 8, and 12 hours by

multiplying the PID score at each post-dose time point by the duration (in hours) since the preceding time point and then summing these values over 2, 4, 8, and 12 hours, respectively.

Similarly, Total Pain Relief Scores (TOTPARs), will be calculated by multiplying the pain relief score at each post-dose time point by the duration (in hours) since the preceding time point and then summing these values.

In all analyses for participants who take rescue medication, all pain intensity scores after intake of rescue medication will be imputed by the worse of the baseline or the score assessed immediately before taking rescue medication. All pain relief after intake of rescue medication will be imputed by “no relief” (0).

Endpoint	Statistical Analysis Methods
Primary	
The primary efficacy analyses population will be based on the PP population.
 
Sum of Pain Intensity Difference over 8 hours: SPID0-8 be analyzed using an analysis of covariance model (ANCOVA) with treatment as fixed effect and baseline pain intensity score as the covariate. A 95% of confidence interval (CI) for the treatment differences and pairwise p-values will be calculated based on the above mentioned model.

Secondary	
Total Pain Relief over 8 hours: TOTPAR0-8 will be analyzed similarly as for the primary endpoint.
 
Time to first use of rescue medication. If a participant did not take the rescue medication during the treatment period, (s)he will be censored at the time of last assessment. Time to first use of rescue medication will be estimated and plotted using Kaplan-Meier method and analyzed using log-rank test.

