5. EFFICACY AND SAFETY ENDPOINTS

5.1 Efficacy Endpoints

5.1.1 Primary Efficacy Endpoints

The primary efficacy endpoint is the Sum of Pain Intensity Difference over 8 hours (SPID0-8).

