6.1.9 Use of an Efficacy Subset of Subjects

The PP population will be used for the primary analysis.

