6.8 Analysis of Efficacy

CCI

CCI

For the purposes of analysis, dates of the subject assessments for efficacy will be populated programmatically when the time indicates a date change, i.e., the collection time of the time point went past midnight.

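### The primary (PP) population requires 12-hour completion although SPID0-8 is settled at hour 8, so events in hours 9-12 can remove complete primary-endpoint data

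*Protocol*

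**What the plan says.** **Endpoint.** Protocol 9.1: "The primary efficacy endpoint is the sum of change in pain intensity from 0 to 8 hours". SAP 5.1.1 names the same endpoint. Under Protocol 9.4.1 and SAP 6.8.1, SPID0-8 is a sum of pain intensity differences, each weighted by the time since the preceding assessment, and the sum stops at hour 8.

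**Population.** Protocol 9.4.1: "The primary efficacy analyses population will be based on the PP population". SAP 6.1.9: "The PP population will be used for the primary analysis". Protocol 9.3 admits to PP those ITT participants "who do not have any major protocol violations and complete the 12 hour assessments". It gives ITT a secondary role, as a sensitivity analysis for selected parameters.

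**SAP text not visible.** The SAP's population definitions, its missing-data rule and part of its section on changes to the planned analyses are blacked out. Whether the SAP repeats the 12-hour clause cannot be checked.

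**Timetable.** The Schedule of Activities (Protocol 1.3) places surgery between 05:30 and 10:30 and has the row "Discharge from Unit the evening of Day 1". Protocol 8.1.6: "Participants who have not met the randomization criteria within 4.5 hours from last suture or 14:30 h will not be randomized". Protocol 4.1 requires everyone to stay and complete all assessments whether or not they take rescue. Protocol 6.7 puts discharge after the 12-hour assessments, and 8.1.6 puts it after all trial procedures. SAP 6.8 advances the assessment date "when the time indicates a date change, i.e., the collection time of the time point went past midnight".

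**The concern.** A condition for entering an analysis set should relate to the question that set answers. Here the question closes at hour 8 but the condition runs to hour 12. In between, a participant may withdraw, stop because of an adverse event, or fail to complete assessments. None of this changes the SPID0-8 value, yet it decides whether that value is used.

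Completion is observed after randomisation and could be related to treatment. Selecting on it puts the randomised comparison at some risk, and the hour-8 question gains nothing in return. The direction of any bias cannot be worked out from the documents. The same reasoning applies to TOTPAR0-8 and to the 0-2 and 0-4 hour sums. The caffeine and placebo arms are planned at 15 evaluable participants each, so one lost participant is 1/15 = 6.7% of such an arm.

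**Working it through.** **1. Does any rating after hour 8 enter SPID0-8?** The formula is SPID0-8 = sum over assessments t from 0.5 h to 8 h of PID(t) × (hours since the preceding assessment). The last term is at hour 8, so ratings at hours 9 to 12 have no weight. For a participant who has taken rescue, Protocol 9.4.1 fills later intensity scores by rule, so that participant's value is also fixed by hour 8.

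**2. Who is removed?** Take a participant with all ratings through hour 8 who leaves at hour 9. SPID0-8 is complete. The 12-hour assessments are not complete, so the participant is out of PP and out of the primary ANCOVA, but still in ITT. This holds whether the clause means the hour-12 assessment alone or every assessment through hour 12. Rescue after the first 60 minutes does not trigger this clause by itself, because rescued participants stay and continue their assessments. Rescue at or before 60 minutes is a separate exclusion.

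**3. The plan's own numbers.** Inputs from Protocol 9.2: 180 evaluable and 5% drop-out. 180 / 0.95 = 189.5, rounded up to 190, which agrees with the stated figure of about 190. The seven-term allocation in Protocol 6.1.1 (2:2:2:2:2:1:1, sum 12) gives 180 × 2/12 = 30 and 180 × 1/12 = 15, the stated arm sizes. The ratio printed in 9.2 has six terms and does not fit seven arms.

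**4. Size of the effect.** Let k be the number with complete 0-8 hour data who fail only the 12-hour condition. The documents do not give k. I assume a range of 0 to 10, where 10 means that the whole drop-out allowance (190 − 180) falls after hour 8. Ending the condition at hour 8 would give 180 + k participants, with n = (180 + k) × 2/12 per larger arm and m = (180 + k)/12 in each of the caffeine and placebo arms. No SD is stated, so precision is in SD units:

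- active versus active: SE/SD = √(2/n)
- active versus placebo: SE/SD = √(1/n + 1/m)

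| k | n | m | active vs active | active vs placebo | share of complete 0-8 h data excluded, k/(180 + k) |
|---|---|---|---|---|---|
| 0 | 30.0 | 15.0 | 0.258 | 0.316 | 0% |
| 2 | 30.3 | 15.2 | 0.257 | 0.315 | 1.1% |
| 5 | 30.8 | 15.4 | 0.255 | 0.312 | 2.7% |
| 10 | 31.7 | 15.8 | 0.251 | 0.308 | 5.3% |

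**5. Clock check on the discharge row.** Hour 8 is dose time + 8 h, and hour 12 is dose time + 12 h.

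| Dose | Hour 8 | Hour 12 |
|---|---|---|
| 10:00 | 18:00 Day 1 | 22:00 Day 1 |
| 12:00 | 20:00 Day 1 | 00:00 Day 2 |
| 13:00 | 21:00 Day 1 | 01:00 Day 2 |
| 14:30 | 22:30 Day 1 | 02:30 Day 2 |

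Dosing after noon is possible for any last suture after 12:00 − 4.5 h = 07:30. In those cases an evening discharge on Day 1 and an hour-12 assessment cannot both happen. Hour 8 falls on Day 1 in every case shown, up to the 14:30 qualification limit.

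**The case against.** **A single completer set has a purpose.** Several endpoints run to hour 12 (SPID0-12, TOTPAR0-12, TOTPAR8-12, rescue use over 12 hours), and one set keeps the same people in every table. This is a fair reason for the 12-hour condition on those endpoints. It does not justify the condition for a sum that ends at hour 8.

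**The effect is small, and ITT keeps the data.** Both are largely true. The stay is supervised and in-house, and Protocol 7.2 expects withdrawal to be uncommon. The 5% allowance covers all causes at any time and is already built into the 180, so k = 10 is a ceiling and not a forecast. But ITT is only a sensitivity analysis for selected parameters, so the primary estimate still omits these participants.

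**An hour-8 condition is still a completer rule.** This stands: someone who leaves at hour 7 remains excluded. The change removes only the part of the selection that is unrelated to the endpoint.

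**A stronger reading that the documents do not support.** A reader might infer that the evening-discharge row sends participants dosed late home before hour 12, so that their data are foreseeably lost. Protocol 4.1, 6.7 and 8.1.6 tie departure to completing the assessments, the Schedule of Activities' own footnotes call for assessments at 12 hours, and SAP 6.8 provides for ratings past midnight. Nothing in the text directs discharge between hours 8 and 12, and nothing shows that late-dosed participants are more exposed to exclusion.

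**Conclusion.** The mismatch is real and explicit in the protocol: membership of the primary population depends on four hours that the primary endpoint does not use. Participants with complete SPID0-8 data can be excluded from the primary analysis by what happens in those hours.

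The likely size is modest. Under the assumed range of 0 to 10 of 190, between 0% and 5.3% of those with complete 0-8 hour data are excluded. The largest gain in SE/SD from keeping them is 0.258 to 0.251 for active versus active and 0.316 to 0.308 for active versus placebo. These figures assume that losses fall in proportion to the allocation ratio. They describe precision only, and bias cannot be quantified. The conclusion rests on the protocol wording, because the SAP's PP definition is redacted.

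The discharge row is a separate labelling inconsistency. It conflicts with an hour-12 assessment for anyone dosed after noon, but it is not evidence of data loss. The point is worth acting on because the correction is cheap, not because the expected effect is large.

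**What to change.** In Protocol 9.3, and in the SAP's PP definition if it carries the same clause, replace the fixed 12-hour condition with completion of assessments through the end of the window being analysed:

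- hour 8 for SPID0-8 and TOTPAR0-8
- hour 2 or hour 4 for the corresponding shorter sums
- hour 12 for the 0-12 and 8-12 hour sums

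Show the PP size in each efficacy table. The cost is one clause and PP sizes that differ slightly between endpoints. No additional participants, visits or data are needed.

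Separately, reconcile the discharge row in Protocol 1.3 with Protocol 4.1, 6.7 and 8.1.6 and with SAP 6.8, so that all five places describe the same timetable. Which timetable applies is for the sponsor and the investigator to settle.

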### 2.3 Benefit/Risk Assessment

Participants who need to have third molar extraction will be solicited to participate in this study. Participants who consent to participate may benefit by receiving a medical exam, dental radiographs and no-cost surgical procedures for teeth extraction. Furthermore, post-surgical participants will be provided continuous nursing care for approximately 12 hours after surgery. Potential risks of the surgical procedure include pain, dry socket, infection, swelling, bleeding, trismus, and lip or tongue numbness. Potential risks related to local anesthesia and mild sedation include paresthesia and drowsiness. Participants who experience a treatment failure can have the option of taking a standard rescue medication commonly used for post-operative pain relief. Potential study medication benefit will be relief of postsurgical pain, which is highly

prevalent following extraction of wisdom teeth. Potential risks of a single dose of OTC study medication are low and described in the Drug Facts Label.

During the study, participants will be closely monitored for evidence of adverse events. Weighing between the potential risks associated with the study, and given the ability to mitigate risks through close monitoring and routine peri-operative care, this study is considered clinically and ethically acceptable.

More detailed information about the known and expected benefits and risks and reasonably expected adverse events may be found in the naproxen sodium Investigator's Brochure and Aleve® Drug Facts Label.

CCI

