#### Treatment Phase

Following selection, qualified participants will enter the Treatment Phase and be scheduled for their surgical teeth extractions. After completion of the surgical teeth extractions, participants will remain at the study site for observation. Participants with appropriate pain requirement will be randomized into one of seven (7) treatment groups. Participants will rate their pain severity and pain relief over the next 12 hours. Onset of analgesia will be measured using a two stopwatch approach. The first stopwatch will be used to capture the time when any pain relief is first perceived and in certain cases, the second stopwatch will be used to capture the time when pain relief becomes meaningful to the participant. After completion of all trial procedures, participants will be discharged from the study site.

All participants are required to remain at the study center and complete all assessments regardless of rescue.

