Many studies of caffeine as an analgesic adjuvant show its effectiveness when used at a dose of [REDACTED] (Sawynok and Yaksh 1993, Derry, Derry et al. 2014, Weiser, Richter et al. 2018). In a Cochrane Review of randomized controlled trials, the effectiveness of single dose caffeine as an adjuvant to analgesics such as APAP, ibuprofen, aspirin, or combination of APAP and aspirin was examined for relief of acute pain (Derry, Derry et al. 2014). [REDACTED] caffeine was the most effective adjuvant dose regardless of the pain condition or analgesic. Up to 10% more patients achieved pain relief at 50% of maximum relief.

Derry *et al* have also published a Cochrane review of the effectiveness of ibuprofen combination with caffeine on post-operative pain. They identified five randomized double blind placebo/active controlled studies with single dose treatment, which fit the selection criteria. A total of 1501 subjects were included in the analysis. Most studies used either 100 or 200 mg caffeine in the combination product. The combination products of [REDACTED] caffeine with either 100 or 200 mg of ibuprofen resulted in more subjects experiencing at least 50% pain relief over six hours as compared to placebo/active. The re-medication rate was also decreased in the groups using the combination products.

In addition to the data pointing to the effectiveness of caffeine [REDACTED] or above, preclinical studies suggest that low levels of caffeine may inhibit the anti-nociception effect of various analgesics (Sawynok and Yaksh 1993).

Based on all the above mentioned efficacy considerations, BHC is proposing to conduct a dose ranging study with [REDACTED] doses of caffeine: [REDACTED]

[REDACTED] amounts of caffeine, [REDACTED] exhibit a positive safety profile, and [REDACTED] also possess a positive benefit/risk balance.

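### The primary SPID0-8 analysis drops everyone who rescues within 60 minutes, so its population is selected on an efficacy outcome that the plan already scores

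*Protocol*

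**What the plan says.** Protocol section 9.3 defines three nested populations. Of the PP set it says "PP population will be used as the primary analysis for the efficacy parameters", and of ITT "ITT population will be used as secondary to conduct the sensitivity analysis for the selected parameters". Section 9.4.1 repeats that the SPID0-8 ANCOVA is run on PP, and SAP 6.1.9 agrees: "The PP population will be used for the primary analysis".

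Membership of PP depends on what happens after dosing. Section 9.3 states: "Any participant who rescues or vomits at or prior to 60 minutes after ingesting study medication will be excluded from the PP population". It also requires completion of the 12-hour assessments.

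Elsewhere the protocol provides for participants who rescue:

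- Section 6.5.1 permits rescue at any time. Waiting 2 hours is encouraged but not required. Pain is rated immediately before the first rescue dose.
- Section 4.1 (Treatment Phase) keeps them under observation: "All participants are required to remain at the study center and complete all assessments regardless of rescue".
- Section 9.4.1 gives them a score: "In all analyses for participants who take rescue medication, all pain intensity scores after intake of rescue medication will be imputed", using the worse of the baseline score and the score taken just before rescue.

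Time to first rescue and the cumulative proportion rescued are secondary efficacy endpoints (Protocol sections 3 and 9.4.1; SAP 5.1.2).

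**The concern.** The protocol treats rescue as a sign that treatment has not worked. Section 2.3 says: "Participants who experience a treatment failure can have the option of taking a standard rescue medication". Excluding early rescuers therefore removes people because of their efficacy result. The comparison is then among participants who got through the first hour without rescue, and that subset can differ between arms even though the randomised groups did not.

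Rescue can plausibly depend on treatment. Section 4.3, summarising a review of ibuprofen with caffeine, reports: "The re-medication rate was also decreased in the groups using the combination products". That evidence concerns another analgesic and is not specific to the first hour, so it shows only that the possibility is real.

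Vomiting within 60 minutes is also a post-randomisation event that may depend on treatment. It is not analgesic failure in itself, and those participants would keep their observed scores.

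At stake is the choice of caffeine dose, which rests on pairwise differences, confidence intervals and p-values from this model. If the rescue endpoints are also run on PP, as the general wording of section 9.3 implies, their first hour is empty by construction.

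**Working it through.** **Plan's own figures.** Five arms of 30 and two of 15 give 5 × 30 + 2 × 15 = 180 evaluable. Then 180 / 0.95 = 189.5, rounded up to 190 randomised. Both match Protocol section 9.2. No power, SD, effect size or rescue rate is stated.

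**Score of an early rescuer (from the documents).** Baseline NRS b is 5 to 10 (inclusion criterion 9). The SPID0-8 time weights are 0.5 h × 4 (0.5, 1, 1.5, 2 h) and 1 h × 6 (3 to 8 h), which sum to 8 h. After rescue the imputed pain is max(b, s), where s is the pre-rescue score, so PID = b − max(b, s) ≤ 0.

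| Case | Highest SPID0-8 |
|---|---|
| No rescue | 8b |
| Rescue at 61 min | 0.5b + 0.5b = b |
| Rescue at 60 min, 1 h score taken first | 0.5b + 0.5b = b |
| Rescue after the 0.5 h but before the 1 h assessment | 0.5b |

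So a rescuer at or before 60 minutes reaches at most b / 8b = 12.5% of the maximum. The absolute range is −40 (b = 5, pain 10 throughout: −5 × 8) to +10 (b = 10). The 60-minute and 61-minute rescuers have the same ceiling, but the first is deleted and the second is kept as a failure.

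**Effect of one deletion (means assumed).** If the deleted participant would score 0 and the others average μ, an arm of 30 gains μ/30 (0.33 to 1.0 for μ of 10 to 30). An arm of 15 gains μ/15 (0.33 to 1.33 for μ of 5 to 20).

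**Effect on a treatment difference (means and rates assumed).** Let p be the early-rescue rate and μ the mean among the rest, for test (T) and comparator (C), with early rescuers scoring 0:

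- PP difference = μT − μC
- All-participant difference = (1 − pT)μT − (1 − pC)μC
- PP minus all-participant = pT·μT − pC·μC

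With μT = 22 (combination) and μC = 20 (naproxen sodium), the PP difference is 2.0 throughout:

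| pT, pC | All-participant difference | PP minus all-participant |
|---|---|---|
| 0%, 10% | 22 − 18 = 4.0 | −2.0 |
| 2%, 5% | 21.56 − 19 = 2.56 | −0.56 |
| 5%, 5% | 20.9 − 19 = 1.90 | +0.10 |
| 5%, 2% | 20.9 − 19.6 = 1.30 | +0.70 |
| 10%, 0% | 19.8 − 20 = −0.2 | +2.2 |

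The sign changes at pT/pC = μC/μT. That is 20/22 = 0.91 here, and 5/20 = 0.25 for assumed means of 20 against 5 on placebo. A wider set of assumptions (means 24 v 8, 24 v 20 and 26 v 24; early rescue 0 to 15% in the test arm and 0 to 40% in the comparator) gave shifts from −7.0 to +3.2.

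**Type I error.** In a two-arm ANCOVA simulation (4,000 runs per scenario, rescue model assumed), identical arms gave rejection rates of 0.046 to 0.054 with everyone kept and 0.045 to 0.051 in PP. The exclusion does not inflate error under a strict null. It changes what is estimated when early rescue differs between arms.

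**Rescue endpoints, if run on PP.** Cumulative rescue at 0.5 h and 1 h is 0% in every arm. A true 12-hour proportion R becomes (R − p)/(1 − p). For p of 2 to 10%, an assumed R of 50% becomes 49.0 to 44.4%, and 80% becomes 79.6 to 77.8%.

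**The case against.** The strongest reply is that no consequence can be shown from the documents. Only the 12.5% ceiling comes from them. The shifts rest on assumed means and rates, and the ends of the ±2 range need no early rescue in one arm and 10% in the other, although both arms contain naproxen sodium. With equal rates of 5% the shift is 0.10. With assumed means of 20 and 5 against placebo, rates of 2% and 10% give 0.4 − 0.5 = −0.1. The encouragement to wait 2 hours may also keep early rescue uncommon. All of this stands, and it limits what can be said about size.

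A second reply is that someone who rescues or vomits within an hour has not given the dose time to act, and that the rule is pre-specified and blinded. Pre-specification prevents data-driven exclusions, but it does not remove selection on an outcome. The rationale also does not fit the cut: participants who rescue between 61 and 119 minutes did not wait 2 hours either, yet they are kept and scored as failures.

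A third is that an ITT sensitivity analysis is planned. It covers only unnamed parameters, and nothing legible says SPID0-8 is among them. SAP 6.4 and parts of 6.8 and 8 are blacked out, so this cannot be settled, nor can the SAP's own PP criteria or the population for the rescue endpoints. The point therefore rests on the protocol text and SAP 6.1.9. SAP 6.7 does summarise rescue medication in each population, but by drug class and name, not by time. Even with an ITT sensitivity analysis, the primary result would still be the selected one.

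**Conclusion.** The concern holds. The primary analysis of SPID0-8 is restricted by a post-randomisation efficacy outcome, and the restriction is unnecessary because those participants are observed and scored. They would also belong to ITT, since the rating taken just before rescue supplies a post-dose pain assessment.

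The documents fix one quantity: the deleted rescuers could score no more than 12.5% of the maximum. The effect on any treatment difference is unknown in size and sign. Under the main assumptions above it ranges from −2.0 to +2.2 against an assumed PP difference of 2.0, and it is close to zero if early rescue is rare or similar across arms.

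This is an unpowered dose-ranging study, so the exclusion could bias dose selection; it does not undermine a confirmatory claim. It should be corrected before database lock.

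**What to change.** 1. In Protocol 9.3 and 9.4.1 and SAP 6.1.9 and 6.8, make the existing ITT population primary for SPID0-8 and the other efficacy endpoints, with the section 9.4.1 rescue imputation unchanged. This also removes the condition of completing 12 hours from the primary analysis.
2. In SAP 6.8.2.2 and 6.8.2.9, state that time to first rescue and cumulative rescue are analysed on ITT.
3. Keep PP, with its 60-minute rule, as a supportive analysis.
4. Reconcile Protocol 6.3.2, which drops unblinded participants from the ITT analysis, with the ITT definition in 9.3, so that unblinding does not remove people from what would become the primary set.

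The cost is protocol and SAP wording before lock, plus any ITT tables not already planned. The 180 and 190 figures and data collection are unchanged. A small downside is that a few participants who vomited the dose stay in and may slightly dilute the effect; the supportive PP analysis would show by how much. Only naming SPID0-8 and the rescue endpoints among the ITT sensitivity analyses would be cheaper and would expose a selection effect, but it would leave the primary estimate subject to it.
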